7.2 NULL AND ALTERNATIVE HYPOTHESES

The primary hypotheses are that BI 655066 is different than placebo in achieving $\geq 90\%$ reduction from baseline in the Psoriasis Area and Severity Index score (PASI 90) and sPGA of 0 or 1 at Week 16 in participants with moderate to severe chronic plaque psoriasis. For the primary analyses, this study has 2 treatment arms:

Arm 1 – Patients randomised at visit 2 to receive 150 mg of BI 655066
Arm 2 – Patients randomised at visit 2 to receive placebo

For Part B of the trial, patients randomised to receive BI 655066 at visit 2 and have an sPGA response of 0 or 1 at Week 28 will be re-randomised to one of the following treatment arms:

Arm A – Patients re-randomised to continue to receive BI 655066 during Part B
Arm B – Patients re-randomised to receive placebo during Part B

The following null hypotheses will be tested in a hierarchical order using two-sided tests with a type I error of 0.05. The two co-primary endpoints need to be significant simultaneously, therefore no alpha adjustment is necessary.

1. BI 150 mg (Arm 1) is not different from placebo (Arm 2) with respect to PASI 90 or sPGA 0 or 1 response at Week 16
2. BI 150 mg (Arm 1) is not different from placebo (Arm 2) with respect to PASI 75 response at Week 16
3. BI 150 mg (Arm 1) is not different from placebo (Arm 2) with respect to PASI 100 response at Week 16
4. BI 150 mg (Arm 1) is not different from placebo (Arm 2) with respect to achieving an sPGA score of clear (0) at Week 16
5. BI 150 mg (Arm 1) is not different from placebo (Arm 2) with respect to achieving a DLQI score of 0 or 1 at Week 16.

For the re-randomized patients, the following null hypothesis will be performed with a type I error of 0.05.

- Arm A (patients re-randomised to BI 655066) is not different from Arm B (patients re-randomised to placebo) with respect to sPGA 0 or 1 response at Week 52.

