7.5 HANDLING OF MISSING DATA

Every effort should be made to collect complete data at all visits.

The following rules will be used to impute for missing data:

- For all non-binary endpoints, last observation carried forward (LOCF) will be used to impute missing values
- For all binary endpoints (i.e. endpoints that are either 1 (patient responded) or 0 (patient did not respond)):
 - If no data after that visit*, then impute as failure (NRI [No Response Imputation])
 - If data at visits* before and after, only impute as success if both visits are successes; else impute as failure

* Patients that take prohibited medications to treat Psoriasis will be treated the same as those that discontinued from the trial – i.e. subsequent visits following start of prohibited medication will be considered as failure for binary endpoints.

Missing items from the PRO questionnaires will be handled according to the measure instructions ([Section 10.7](#)). If there is no data for a particular visit, then it will be imputed following the same rules as described above.

Sensitivity analyses to assess the robustness of the hypothesis testing results will include the following methods where applicable:

- LOCF (for binary endpoints)
- Logistic regression

- Mixed effect Model Repeat Measurement (MMRM) (for continuous endpoints)
- Multiple imputation (for binary endpoints)

Of note, for randomized withdrawal analyses, subjects who received retreatment will be counted as non-responders in all visits after the date of retreatment.

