7.7 DETERMINATION OF SAMPLE SIZE

This study is designed to show a difference between BI 655066 and placebo in terms of PASI90 response and sPGA scores of clear or almost clear at Week 16. However, this study was also powered to show a difference in sPGA response at Week 52 between the patients randomized to continue on BI 655066 vs. patients randomized to placebo at Week 28.

Based on the interim results from 1311.2 ([c03272682-01](#)), it is assumed at most 10% of the patients in the re-randomized BI 655066 arm will lose sPGA response of clear or almost clear (0 or 1) at Week 52 whereas approximately 25% of patients in the re-randomized placebo arm will lose response. Using a 1:2 re-randomisation scheme (BI 655066:placebo), 102 patients in the BI 655066 arm and 204 patients in the placebo arm will provide at least 90% power to detect the difference in sPGA response rate at Week 52. Assuming that 80% of patients on BI 655066 at baseline will achieve sPGA of clear or almost clear at Week 28, the total sample size required for the initial BI 655066 arm at Visit 2 is $(102)(3) \div 0.8 = 383$. See [Table 7.7:1](#) for more sample size calculations to have at least 90% power.

Table 7.7:1 Sample sizes for randomized withdrawal comparison

Response Rate at Week 52			Randomisation ratio at Week 28 active:placebo = Total N	Total N at randomisation
Active	Placebo	Delta	1:2	
90%	72.5%	17.5%	79:158 = 237	297
90%	75%	15%	102:204 = 306	383
90%	77.5%	12.5%	138:276 = 414	518

Calculated using ADDPLAN Version 6.0.4.

Thus 400 patients in the original BI 655066 arm, provide at least 90% power for the randomized withdrawal comparison. Using a 4:1 randomisation will yield a total sample size of 500 = 400:100 for BI 655066: placebo.

Based on the outcome from trials 1311.1 and 1311.2, the PASI90 response rate at Week 16 is assumed to be at least 65% in the BI 655066 arm and approximately 5% for placebo. For sPGA clear or almost clear at Week 16, the response rate for the BI 655066 arm is assumed to be at least 80% and approximately 5% for placebo. This trial will have >99% power for comparing each BI 655066 arm to placebo on both of these endpoints.

All calculations were performed using ADDPLAN Version 6.0.4, an Aptiv Solutions Company.

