b. The minimum of upper bound, the first dose date of retreatment with risankizumab for relapsed subjects (except the additional analysis as in footnote a), and within 105 days of last dose of study drug for safety analyses. If time is collected in vital signs, restrict to records prior to the first dose of retreatment.

Note: For additional PASI and sPGA analysis on ITT_B_R subjects re-randomized to risankizumab to evaluate continuous treatment, evaluations after retreatment with open label risankizumab will also be included along with blinded assessments.

Table 9. Visit Windows for Analysis of Safety Laboratory Tests and ECG in Part B (Safety_B_R/Safety_B_NR Populations)

Window Label	Target Day	Interval
Entry of B	1	≤ 1
Week 40	85	[2, 127]
Week 52	169	[128, 211]
Week 64	253	[212, 295]
Week 76	337	[296, 379]
Week 88	421	[380, 477]
Week 104	533	[478, 589 ^a]

Rx Day calculated relative to the first dose date of study drug in Part B. For re-randomized subjects not dosed in Part B, Rx Day calculated relative to the IRT date of Re-randomization evaluation.

a. The minimum of upper bound and first dose date of retreatment with risankizumab for relapsed subjects (and within 105 days of last dose of study drug for safety analyses).

Table 10. Visit Windows for Analysis of Other Efficacy Endpoints Only Collected at Week 52, 76, and 104 in Part B (ITT_B_R/ITT_B_NR/PP_B_R Populations)

Window Label	Target Day	Interval
Entry of B	1	≤ 1
Week 52	169	[2, 253]
Week 76	337	[254, 435]
Week 104	533	[436, 631 ^a]

Rx Day calculated relative to the first dose date of study drug in Part B. For re-randomized subjects not dosed in Part B, Rx Day calculated relative to the IRT date of Re-randomization evaluation.

a. The minimum of upper bound and first dose date of retreatment with risankizumab for relapsed subjects.

Table 11. Visit Windows for Analysis of PASI and sPGA Across Part A2 and B (ITT_ARM2 Population)

Window Label	Target Day	Interval
Entry of A2	1	≤ 1
Week 20	29	[2, 43]
Week 24	57	[44, 71]
Week 28	85	[72, 99]
Week 32	113	[100, 127]
Week 36	141	[128, 155]
Week 40	169	[156, 183]
Week 44	197	[184, 211]
Week 48	225	[212, 239]
Week 52	253	[240, 274]
Week 58	295	[275, 316]
Week 64	337	[317, 358]
Week 70	379	[359, 400]
Week 76	421	[401, 442]
Week 82	463	[443, 484]
Week 88	505	[485, 526]
Week 94	547	[527, 582]
Week 104	617	[583, 652]

Rx Day calculated relative to first dose date of risankizumab.

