10.1.4 Missing Data Imputations

Missing data will be imputed using the following methods for the efficacy analyses:

- Non-Responder Imputation (NRI): the NRI analysis will categorize any subject who does not have evaluation during a specific visit window as a non-responder for that visit. The only exception is when the subject is a responder both before and after a specific visit window, then the subject will be categorized as a responder for the visit. Only observations within the same analysis period will be used except for summary of ITT_A2 from ARM 1, where subjects' observation from Part A1 can be used since the treatment is the

same. The NRI will be the primary approach in the analyses of categorical variables.

- Last Observation Carried Forward (LOCF): The LOCF analyses will use the last observed non-missing evaluation (last completed non-missing evaluation, from composite endpoint) from the previous visit within the particular period for efficacy measures assessed to impute missing data at later visits in the same period. Baseline efficacy evaluations will not be carried forward. Of note, post-baseline observations from Part A1 can be carried forward to ITT_A2 subjects from ARM 1 since treatment is the same. LOCF will be the primary approach in the analyses of continuous variables, and the secondary approach in the analysis of categorical variables.
- As-Observed Cases (OC): The as-observed analysis will not impute values for missing evaluations, and thus a subject who does not have an evaluation on a scheduled visit will be excluded from the as-observed analysis for that visit. As-observed analysis will be the secondary approach in the analysis of continuous variables.
- Multiple Imputation (MI): The MI will be used as sensitivity approach to impute missing data in primary and ranked secondary endpoints. The variables to be included in the imputation model are listed below. If MI is not applicable due to the nature of our data (e.g., MCMC algorithm does not converge), logistic regression or mixed effect model repeat measurement (MMRM) methods will be applied as sensitivity approach, whichever applicable.

The Multiple Imputation analysis will be carried out in three steps.

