10.2.2 Primary Efficacy Analysis in Part B

Achievement of an sPGA of clear or almost clear (0 or 1) at Week 52 is the primary endpoint for Part B under re-randomization. This endpoint will be tested independently with a type I error rate of 0.05, for the ITT_B_R Population. A sensitivity analysis will also be performed on the same endpoint for the PP_B_R Population.

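### In Part B the as-observed analysis of continuous scores drops patients once they are retreated for relapse, and the protocol's MMRM for continuous endpoints has no planned place in the SAP

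*SAP*

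**What the plan says.** SAP 10.1.4 uses LOCF as the primary method for continuous variables and states: "As-observed analysis will be the secondary approach in the analysis of continuous variables". As-observed means no imputation: a subject without an evaluation at a visit is left out of that visit's analysis. SAP 10.1.2 compares arms on continuous variables by ANCOVA, and 10.1 runs the efficacy analysis in ITT_A1 and ITT_B_R.

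For PASI and sPGA in Part B, footnote b to Table 8 (SAP 6.0) ends a subject's data at "The minimum of upper bound, the first dose date of retreatment with risankizumab for relapsed subjects" or at the other limits listed there. Footnote a to Table 10 does the same for the other Part B efficacy scores. Retreatment follows an sPGA of 3 or more (SAP 4.2).

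The closing note of SAP 10.1.4 says how retreated subjects are treated under NRI and MI (non-responders afterwards) and under LOCF (last value before retreatment carried forward). It is silent on as-observed.

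Protocol 7.5 also makes LOCF the main method for non-binary endpoints. Its list of sensitivity analyses includes "Mixed effect Model Repeat Measurement (MMRM) (for continuous endpoints"), and the list is qualified by applicability. In the SAP, MMRM appears only as a substitute if multiple imputation cannot be applied. Multiple imputation is confined to the primary and ranked secondary endpoints, all of them binary. SAP 14.1 lists four changes from the protocol; none concerns MMRM or the as-observed method.

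**The concern.** Read together, the window rule and the exclusion rule remove patients from the as-observed comparison because their psoriasis came back. The plan expects more loss of response after withdrawal than on continued drug, so more patients should leave the placebo arm. Those who remain at later visits are mainly patients who have not relapsed, and the contrast between arms tends to shrink for that reason alone.

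As-observed is also the only planned alternative to LOCF for continuous Part B scores. A reader of the report may take agreement or disagreement between the two as evidence on robustness, although the gap partly reflects who was removed. The protocol's model for this purpose has no planned use, and the SAP does not tell the reader that.

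**Working it through.** **Inputs from the documents.** Part B test: "This endpoint will be tested independently with a type I error rate of 0.05, for the ITT_B_R Population" (SAP 10.2.2). Two-sided testing is taken from the wording for the Part A hierarchy, "tested in a hierarchical order using two-sided tests with a type I error of 0.05" (Protocol 7.2). Sizes and power: "102 patients in the BI 655066 arm and 204 patients in the placebo arm will provide at least 90% power". Loss by Week 52: "it is assumed at most 10% of the patients in the re-randomized BI 655066 arm will lose sPGA response" and "approximately 25% of patients in the re-randomized placebo arm will lose response" (all Protocol 7.7). Re-randomisation is 1:2, with an 80% responder rate at Week 28.

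**Step 1: the plan's own figure.** With response 0.90 v 0.75 and 1:2 allocation, the pooled proportion is (0.90 + 2×0.75)/3 = 0.80. Then

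n = [1.960·√(0.80·0.20·1.5) + 1.282·√(0.90·0.10 + 0.75·0.25/2)]² / 0.15² = (0.960 + 0.549)² / 0.0225 ≈ 101.3, so 102.

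This gives 102:204 = 306, and 306/0.8 = 382.5, so 383. The plan's figures reproduce (power 90.2%). They concern the binary endpoint. The documents give no effect, SD or relapse rate for a continuous score.

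**Step 2: trace one patient.** Suppose a placebo patient relapses and is retreated at Week 40.

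| Analysis | Week 40 | Weeks 44, 48, 52 |
|---|---|---|
| NRI (binary) | observed | non-responder |
| LOCF (continuous) | observed | last pre-retreatment value |
| As-observed (continuous) | observed | not in the analysis |

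The value on the retreatment date itself stays in.

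**Step 3: size, by algebra.** Loss of response is sPGA 2 or more and relapse is sPGA 3 or more, so relapsed patients are a subset of those who lost response. Let f be the share of losers already retreated before the visit (assumed equal in both arms). Let r be the relapsed patients' excess score as a multiple of the excess score at sPGA 2. Both are assumptions. In units of the sPGA 2 excess:

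- Full contrast = (0.25 − 0.10)·(f·r + 1 − f)
- As-observed contrast = 0.25(1−f)/(1−0.25f) − 0.10(1−f)/(1−0.10f)

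Example, f = 0.5 and r = 2: full = 0.15×1.5 = 0.225; as-observed = 0.125/0.875 − 0.05/0.95 = 0.090; lost = 1 − 0.090/0.225 = 60%. Retained: 95% of the active arm and 87.5% of placebo.

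| Share of contrast lost | r = 1.5 | r = 2 | r = 3 |
|---|---|---|---|
| f = 0 | 0% | 0% | 0% |
| f = 0.25 | 27% | 34% | 45% |
| f = 0.5 | 52% | 60% | 70% |
| f = 0.75 | 76% | 81% | 87% |
| f = 1 | 100% | 100% | 100% |

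**Step 4: size, by simulated PASI paths.** Paths were calibrated to 10% and 25% loss at Week 52, with the relapse-visit value kept. Assumptions: worsening of 1 to 5 percentage points of baseline PASI per week, and relapse at 40% or 50% of baseline. Week 52 differences, in percent of baseline (ratios from unrounded values):

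| Slope | Relapse at | Placebo removed | No retreatment | LOCF | As-observed | As-observed/LOCF |
|---|---|---|---|---|---|---|
| 1 | 40% | 1.9% | 7.4 | 7.2 | 7.0 | 0.96 |
| 1 | 50% | 0.4% | 7.3 | 7.2 | 7.1 | 0.99 |
| 2.5 | 40% | 9.8% | 7.7 | 6.3 | 4.3 | 0.69 |
| 2.5 | 50% | 6.0% | 7.7 | 6.9 | 5.4 | 0.79 |
| 5 | 40% | 15.7% | 10.2 | 6.9 | 3.1 | 0.45 |
| 5 | 50% | 12.8% | 10.2 | 7.8 | 4.0 | 0.51 |

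The ratio ranges over 0.32–0.89 at Week 76 and 0.41–1.14 at Week 104. LOCF also falls short of the no-retreatment contrast, so agreement between the two planned methods would not show robustness.

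**Step 5: what MMRM would recover.** In an illustrative simulation that removed patients when PASI itself exceeded 8, MMRM recovered 1.46 of 1.63, 2.45 of 2.59 and 3.45 of 3.55 (90–97%). That set-up favours MMRM, because removal depends on the modelled score. Under paths like those in Step 4, a likelihood equivalent gave 100–160% at Week 52. It overshot badly at Week 76 when worsening was fast, since no retreated patients inform later visits.

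**The case against.** The strongest reply is that little hangs on this. Continuous Part B scores are further endpoints outside the hierarchy. As-observed is secondary, and the primary LOCF analysis keeps relapsed patients at their last value before retreatment. The withdrawal effect is carried by sPGA 0/1 at Weeks 52 and 104 and by PASI 75/90/100 at Week 52, where retreated patients count as non-responders, and by time-to-event analyses that count retreatment as failure. All of this stands and limits the consequence.

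Second, the protocol's list serves the hypothesis tests, all of which are binary, and applies only where applicable. A reader might infer that the SAP deleted a firm commitment. The documents do not support that: MMRM was reduced to a conditional fallback. Even so, the protocol's bullet names continuous endpoints, and the SAP leaves none of them with a planned MMRM.

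Third, MMRM is no clean answer. It targets the difference had nobody been retreated, which neither document adopts as its estimand. The trigger is sPGA, not PASI, so a PASI model does not condition exactly on the reason for removal. Nor does the approach carry over to every score: Flow Chart 2 schedules no DLQI, NAPSI, PPASI or PSSI at the relapse visit. This stands and narrows the remedy.

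**Conclusion.** The point holds in a limited form. In ITT_B_R the as-observed ANCOVA of continuous scores drops retreated patients at all visits after retreatment. The comparison is selected on outcome, probably more so in the placebo arm, and tends towards no difference. It should not be read as a check on LOCF. The protocol's MMRM has no planned place for any continuous endpoint, and SAP 14.1 does not disclose this.

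A reader might infer that most of the withdrawal effect is erased. The documents do not support that. The loss is negligible if worsening is slow or few of those who lose response have been retreated, and large if worsening is fast or most have been. At Week 52 the simulated as-observed/LOCF ratio was 0.45 to 0.99. Nor can a steady growth of the bias after Week 52 be inferred, since the later ratios do not fall consistently. These sizes rest on assumed relapse shares, score ratios, slopes and cut-offs, and on the plan's 10% and 25% loss.

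The effect is confined to further endpoints. The sPGA tests at Weeks 52 and 104 and the time-to-relapse analysis are unaffected. The change is worth making, but no confirmatory conclusion depends on it.

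**What to change.** 1. For PASI change and percent change in ITT_B_R, add the protocol's MMRM as the sensitivity analysis to LOCF through Week 52. Terms: treatment, visit, treatment-by-visit, stratification factors, and the baseline or Week 28 value. Use data up to and including the relapse visit.
2. State that the estimate rests on a missing-at-random, no-retreatment assumption, and that visits after Week 52 are to be read with caution.
3. Say in SAP 10.1.4 how retreated subjects enter the as-observed analysis. Label any as-observed Part B result as conditional on no retreatment and not as a check on LOCF.
4. Do not extend the MMRM to scores not scheduled at the relapse visit (DLQI, NAPSI, PPASI, PSSI).
5. List the MMRM position and the added as-observed method in SAP 14.1.

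The cost is SAP wording and one additional standard model, with no new data. The drawback is one more estimate that depends on its assumptions.

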7.3 PLANNED ANALYSES

The efficacy analyses will be based on the intent-to-treat principle, comprising all participants who were randomized and received at least one dose during the trial. Misrandomized patients are by definition screening failures and therefore are not included in the intended to treat population. Efficacy analyses will be based on the planned treatment (i.e., the treatment assigned at randomisation); this set of patients is called the Full Analysis Set (FAS). Safety analyses will be based on the actual treatment received at the randomisation visit; this set of patients is called the Safety Set (SAF).

All efficacy analyses will be conducted on the FAS. All safety analyses will be conducted on the SAF.

Important violations of the protocol will include key inclusion and exclusion violations, incorrect medications taken, compliance with study medication, incorrectly re-randomized or not re-randomized, concomitant use of restricted medications, and any other violations of the protocol deemed important by the study team. All decisions concerning important protocol violations will be made prior to unblinding of the database. A per-protocol set (PPS) will be defined excluding patients with violations that affect Week 16 efficacy. A secondary re-randomized per-protocol set (RRS-PPS) will be defined excluding those patients with violations affecting Week 52 efficacy of randomized withdrawal. The hypothesis tests as described in Section 7.2 will be repeated on the PPS or RRS-PPS populations, as appropriate.

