7.3.3 Further endpoint analyses

Further endpoints will be summarized, with number and proportion of responders for dichotomous endpoints and mean, median, SD and IQR presented for continuous variables.

Time to onset of *Endpoint*, the time to event will be calculated as:

- Time to first onset (with observed event) = [date of first onset] – [date of first active treatment] + 1
- If a patient never attains *Endpoint* (e.g., PASI75 or PASI90), then that patient's time to first onset will be censored at the last visit where the *Endpoint* was measured (e.g., PASI).

Time to Loss of *Endpoint* will only be performed for patients that are re-randomised at Week 28 (i.e., Arms A and B defined in Section 7.2), where day 0 is defined as the date of the Week 16 visit. Time to loss is defined using the following algorithm:

- a) Never attains *Endpoint* (Failure at day 0)
- b) After achieving *Endpoint*, patient will be a failure if they subsequently do not achieve *Endpoint* and either discontinue from the study or switch therapy while still not achieving *Endpoint*. Time to failure will be calculated using date of first failure to achieve *Endpoint*.
- c) Patients that take prohibited meds to treat Psoriasis will be counted as failures at the time when they first take the prohibited med.
- d) Patients that switch therapy while maintaining response will be censored at their last measurement prior to switching treatment. A switch from active medication to Placebo does not constitute a change in treatment.
- e) Patients who maintain *Endpoint* throughout the study will be censored at their last measurement.

Time to Loss of *Endpoint* (from time of achieving *Endpoint* or from specific point in time) will be defined as above but only for those patients that have achieved *Endpoint*.

All Time to Event endpoints will be presented using Kaplan-Meier curves with comparisons made between treatment groups using stratified Log-Rank test. Further information will be provided in the TSAP.

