10.1.3 Analyses of Time-to-Event Variables

Time to first achievement of endpoints will only be performed in ITT_A1 up to Week 16. The time to event will be calculated as:

- Time to first achievement (with observed event) = [date of first achievement] – [date of first dose] + 1
- If a subject never attains Endpoint at the end of evaluation period, that subject's time to first achievement will be censored at the last visit where the variable was measured

Time to loss-of-response (and time to relapse) endpoints will only be performed in ITT_B_R Population among those who achieved response at Re-Randomization. The time to failure events will be calculated as:

- Subjects will be considered as failures if they subsequently lost the response, or discontinue from the study due to AE of "Worsening of disease under study," or receive retreatment with risankizumab.
- Time to failure events = [date of failure] – [date of first dose in Part B] + 1
- Subjects who maintain Endpoint throughout the study, or discontinued from the study due to reasons other than above, will be censored at their last measurement.

Both time to first achieving endpoints and time to loss-of-response endpoints will be analyzed using Kaplan-Meier estimates for each treatment group. In the ITT_A1 and ITT_B_R populations, treatments will be compared using stratified Log-rank test.

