- Imputation of missing data. The imputation will be generated for each efficacy endpoint measurement. The variables to be included in the imputation model are: Baseline disease severity (PASI and sPGA), Baseline weight (continuous variable), treatment group, actual prior TNF antagonist exposure, and measurements at each visit from randomization (or re-randomization) up to the end of the analysis period. For each endpoint, 20 'complete' datasets will be generated using SAS PROC MI. The imputed post-baseline measurements

will be rounded to the same precision as the observed data before the determination of responder status (e.g., PASI 90).

- Analysis of imputed data sets. A CMH test, stratified by stratification factors, will be used to analyze categorical endpoints in each imputed dataset.
- Synthesis of imputation and analysis results. SAS PROC MIANALYZE will be used to generate the final inferences of the risk difference between treatment groups.

Of note, subjects who discontinued due to AE of "Worsening of disease under study," or received retreatment with risankizumab for relapse during Part B, will be counted as non-responders in all visits thereafter in the NRI and MI analyses, and will have their last observation prior to discontinuation or retreatment with risankizumab carried forward in the LOCF analyses.

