14.0 Summary of Changes

14.1 Summary of Changes Between the Latest Version of Protocol and the Current SAP

- Defined analysis populations (including the Per-protocol population) in detail.
- Clarified independent null hypothesis test hierarchy in the ITT Population in Part B consisting re-randomized subjects.
- Added additional ranked secondary endpoint to the ITT Population in Part B consisting re-randomized subjects: achievement of sPGA of clear or almost clear (0 or 1) at Week 104.
- Pre-specified Areas of Safety Interest.

14.2 Summary of Changes Between the Previous Version and the Current Version of the SAP

Updated Table 25, Table 27, and Table 28 based on Integrated Summary of Safety SAP.

Updated the end day for inclusion concomitant medications, based on Integrated Summary of Safety SAP.

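### SAP 10.1.4 leaves out, and 14.1 does not declare as changed, the protocol rule that visits after prohibited psoriasis medication count as failures

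*SAP*

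**What the plan says.** Protocol 7.5 puts patients who take prohibited psoriasis medication on the same footing as those who leave the trial: "subsequent visits following start of prohibited medication will be considered as failure for binary endpoints". Protocol 7.3.3, rule c) of the time-to-loss algorithm, is the counterpart: "Patients that take prohibited meds to treat Psoriasis will be counted as failures at the time when they first take the prohibited med".

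SAP 10.1.4 sets out the working rules. Non-responder imputation (NRI), the primary approach for categorical endpoints, classes "any subject who does not have evaluation during a specific visit window as a non-responder for that visit". The one exception is "when the subject is a responder both before and after a specific visit window", in which case the missing visit becomes a response. A closing note adds two events that force non-response in NRI and multiple imputation (MI): discontinuation for an adverse event of worsening disease, and having "or received retreatment with risankizumab for relapse during Part B, will be counted as non-responders in all visits thereafter".

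For time to loss of response and time to relapse, SAP 10.1.3 begins its list of failures "Subjects will be considered as failures if they subsequently lost the response, or discontinue from the study due to AE of" worsening disease, and ends it with retreatment. Prohibited medication is in neither SAP list. The SAP mentions prohibited treatment only in 7.4, as a protocol-deviation category to be counted. SAP 14.1 lists four changes from the protocol: analysis populations, the Part B test hierarchy, the added Week 104 endpoint and the areas of safety interest.

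**The concern.** The patients concerned can exist. Protocol 3.3.4.1 and 4.2.2.1 let a patient who has used a prohibited medication continue, provided it is stopped. Protocol 6.2.3 also asks patients who stop study drug early to attend the remaining visits. Such patients have observed assessments, so NRI for missing visits does not reach them.

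Under protocol 7.5 they are failures from the start of the medication. Under SAP 10.1.4 as written they are scored on what is observed, and a missing Week 52 visit can become a response through a later visit reached after that medication. A response may then reflect another psoriasis treatment. This affects the Week 16 co-primaries, the Week 52 sPGA 0/1 endpoint (the Part B primary, which also set the sample size) and the ranked Week 104 endpoint.

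**Working it through.** **Is the omission explained elsewhere?** SAP 3.0 cites the protocol dated 28 July 2016. The amendment log for the only later revision, 11 October 2016, shows no change to 7.5 or 7.3.3, so a version difference does not account for it. SAP 10.1.4 carries over the other main elements of 7.5: NRI, the before-and-after exception, LOCF, MI and the retreatment rule.

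**Who is affected at each visit?**
- Week 16: there is no retreatment rule yet, so any user with an observed response is affected.
- Week 52: relapse at sPGA 3 or more triggers open-label retreatment, and later visits are failures under both documents. That leaves users at sPGA 2 or below who remain in the trial.
- After Week 88: relapse retreatment is no longer available, so the Week 52 restriction does not carry over to Week 104.

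**Reproducing the planned figure.** Inputs from protocol 7.7: 90% v 75%, ratio 1:2, at least 90% power; two-sided 0.05 from 7.2. The pooled rate is (0.90 + 2 × 0.75)/3 = 0.80.

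n(active) = [1.960 × √(0.80 × 0.20 × 1.5) + 1.2816 × √(0.09 + 0.1875/2)]² / 0.15² = (0.960 + 0.549)² / 0.0225 = 101.3, so 102, with 204 on placebo. Then 102 × 3/0.8 = 382.5, so 383. Both match the protocol. Power at 102:204 is 90.2%.

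**Effect at Week 52.** Expected re-randomised: 400 × 0.80 = 320, or 107:213. Suppose the protocol rule yields 90% v 75%. If a active and p placebo patients become responders because the rule is absent, the difference moves by a/107 − p/213. One active patient adds 0.93 points and one placebo patient removes 0.47. The shift is zero at p/a = 213/107 = 1.99, that is, for equal shares of each arm.

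- a = 1, p = 5: 15.0 + 0.93 − 2.35 = 13.6 points.
- a = 2, p = 2: 15.0 + 1.87 − 0.94 = 15.9 points.

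**Power.** The planned p-value uses the Greenland–Robins variance, which in one stratum reduces to x(n−x)/n³ + y(m−y)/m³, an unpooled variance. Power is then Φ(d/SE₁ − 1.96). The pooled test, which reproduces the 102:204, gives Φ((d − 1.96 × SE₀)/SE₁).

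- Plan: SE₁ = √(0.09/107 + 0.1875/213) = 0.0415 and SE₀ = 0.0474. Unpooled Φ(1.655) = 95.1%; pooled Φ(1.377) = 91.6%.
- a = 1, p = 5: SE₁ = 0.0399 and SE₀ = 0.0456. Unpooled Φ(1.444) = 92.6%; pooled Φ(1.163) = 87.8%.
- If instead a share f of all planned losers in both arms is re-scored, the difference is 15(1 − f). At f = 0.10 it is 13.5 points, power 92.4% unpooled and 87.5% pooled. At f = 0.20 it is 12.0 points, 88.6% and 82.1%.

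All re-scored counts and shares are assumptions.

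**Week 16.** At 400:100, even 10 extra placebo responders (15% instead of 5%) leave 65% v 15%. SE₁ = √(0.65 × 0.35/400 + 0.15 × 0.85/100) = 0.043 and d/SE₁ = 11.6, so power stays above 99%. The assumed 80% for sPGA 0/1 leaves a wider margin still.

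**The case against.** **Silence is not repeal.** SAP 3.0 says the SAP elaborates the protocol's methods, and nothing in it revokes 7.5. A reader might infer that the two documents now deliberately define different responders. They do not support that; the rule may still be intended. What stands is narrower. SAP 3.0 also says that the SAP guides programming, and a programmer following 10.1.4, which repeats the rest of 7.5, would not apply the rule.

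**Per-protocol sets.** Protocol 7.3 names as important violations "concomitant use of restricted medications, and any other violations of the protocol deemed important by the study team", and the criteria in SAP 5.1 do not mention medication. A reader might take this as a second undeclared omission. It is not: 14.1 lists "Defined analysis populations (including the Per-protocol population) in detail", SAP 5.1 leaves the exclusion criteria open until database lock, and SAP 7.4 counts these patients.

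**Time to event.** Time to loss is a further endpoint outside the ranked tests. Protocol 7.3.3 defers detail to the SAP, and SAP 10.1.3 reworks the whole algorithm. That makes this part secondary. Rule c) also belongs to time to loss only; adding it to time to relapse would count use of a prohibited topical as a relapse.

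**Size and direction.** A patient with an intolerable worsening is discontinued to receive rescue, and with no later visits is a failure anyway. Re-scoring mainly placebo patients shrinks the difference, which works against the sponsor. A reader might still infer a bias in favour of the drug, or a loss of the planned 90% power. Neither is established. The direction depends on the split between arms. In the 1-and-5 and f = 0.10 examples, power falls below 90% only with the pooled test. The 20% share is an assumption, not a bound: it means about 11 placebo patients (0.20 × 0.25 × 213) who used a prohibited drug, had to stop it, and were clear or almost clear at Week 52.

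**Conclusion.** The point holds as an undeclared gap in the SAP's analysis rules: followed literally, 10.1.4 gives a different result from protocol 7.5 for any patient with an observed response after prohibited psoriasis medication. It should be settled before unblinding, because the Week 16 and Week 52 primary endpoints depend on it and a later decision would be post hoc.

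The size is unknown and probably small, since it rests on a usage rate that neither document gives. The Week 16 conclusion is safe. At Week 52 a few re-scored patients move the difference by about a point in either direction, and power by a few percentage points. The power figures assume the planned 90% v 75%, 107:213 re-randomised and, for the unpooled values, a single stratum. No figure in the protocol or SAP is wrong on this point.

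**What to change.** In the closing note of SAP 10.1.4, add subjects who start a prohibited medication to treat psoriasis. They are non-responders at all later visits in NRI and MI, including when the before-and-after exception is applied. In LOCF, carry forward the last observation before that start, in parallel with the retreatment rule.

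In SAP 10.1.3, restore protocol 7.3.3 c) as a failure event for the time-to-loss-of-response endpoints only, not for time to relapse (sPGA 3 or more). If the omission is deliberate, list it in SAP 14.1 with the reason instead.

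The cost is one clause and one bullet, with no protocol amendment. Concomitant and rescue therapies are already recorded in the eCRF (protocol 4.2.1). Someone must agree before unblinding which recorded medications were prohibited and taken for psoriasis; the mild topical steroids allowed on face, axilla or genitalia by the footnote to Table 4.2.2.1:1 do not count. The downside is that brief use of a prohibited topical makes a patient a failure even if the later response is due to study drug. The protocol has already made that choice.
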